- Time Course. Exposure to suspect drug. Has the subject received at least one dose of the suspect drug? Did the AE occur in a reasonable temporal relationship to the administration of the suspect drug?
- Consistency with known drug profile. Was the AE consistent with the previous knowledge of the suspect drug (pharmacology and toxicology) or drugs of the same pharmacological class? Or could the AE be anticipated from its pharmacological properties?
- De-challenge experience. Did the AE resolve or improve on stopping or reducing the dose of the suspect drug?
- No alternative cause can be identified in the subject. The AE cannot be reasonably explained by another aetiology such as the underlying disease, other drugs, other host or environmental factors.
- Re-challenge experience. Did the AE reoccur if the suspected drug was reintroduced after having been stopped? AstraZeneca would not normally recommend or support a re-challenge.
- Laboratory tests. A specific laboratory investigation (if performed) has confirmed the relationship.

In difficult cases, other factors could be considered such as:

- Is this a recognized feature of overdose of the drug?
- Is there a known mechanism?

Causality of 'related' is made if following a review of the relevant data, there is evidence for a 'reasonable possibility' of a causal relationship for the individual case. The expression 'reasonable possibility' of a causal relationship is meant to convey, in general, that there are facts (evidence) or arguments to suggest a causal relationship.

The causality assessment is performed based on the available data including enough information to make an informed judgment. With limited or insufficient information in the case, it is likely that the event(s) will be assessed as 'not related'.

Causal relationship in cases where the disease under study has deteriorated due to lack of effect should be classified as no reasonable possibility.

B 8 Medication Error

For the purposes of this clinical study a medication error is an unintended failure or mistake in the treatment process for an AstraZeneca study drug that either causes harm to the participant or has the potential to cause harm to the participant.

A medication error is not lack of efficacy of the drug, but rather a human or process related failure while the drug is in control of the study site staff or participant.

Medication error includes situations where an error:

- occurred

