The Investigator will remain vigilant for any local laboratory reports where the identification criteria are met, where this is the case the Investigator will:

- Notify the AstraZeneca representative
- Request a repeat of the test (new blood draw) by the central laboratory
- Complete the appropriate unscheduled laboratory CRF module(s) with the original local laboratory test result

When the identification criteria are met from local laboratory results the Investigator will without delay:

- Determine whether the subject meets PHL criteria (see Appendix E 2 for definition) by reviewing laboratory reports from all previous visits (including both central and local laboratory results)

The Investigator will without delay review each new laboratory report and if the identification criteria are met will:

- Notify the AstraZeneca representative
- Determine whether the subject meets PHL criteria (see Appendix E 2 for definition) by reviewing laboratory reports from all previous visits
- Promptly enter the laboratory data into the laboratory CRF

E 4 Follow-up

E 4.1 Potential Hy's Law criteria not met

If the subject does not meet PHL criteria the Investigator will:

- Inform the AstraZeneca representative that the subject has not met PHL criteria.
- Perform follow-up on subsequent laboratory results according to the guidance provided in the Clinical Study Protocol.

E 4.2 Potential Hy's Law criteria met

If the subject does meet PHL criteria the Investigator will:

Determine whether PHL criteria were met at any study visit prior to starting Study treatment (See Section 8.4 Safety Reporting)

- Notify the AstraZeneca representative who will then inform the central Study Team

The Study Physician contacts the Investigator, to provide guidance, discuss and agree an approach for the study subjects' follow-up and the continuous review of data. Subsequent to this contact, the Investigator will:

- Monitor the subject until liver biochemistry parameters and appropriate clinical symptoms and signs return to normal or baseline levels, or as long as medically indicated
- Investigate the aetiology of the event and perform diagnostic investigations as discussed with the Study Physician. << For studies using a central laboratory add: This includes deciding which the tests available in the Hy's law lab kit should be used>>
- Complete the three Liver CRF Modules as information becomes available

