E 6 Actions required when potential Hy's Law criteria are met before and after starting study treatment

This section is applicable to subjects who meet PHL criteria on Study treatment having previously met PHL criteria at a study visit prior to starting Study treatment.

At the first on-study treatment occurrence of PHL criteria being met, the Investigator will determine if there has been a significant change in the subjects' condition[#] compared with the last visit where PHL criteria were met.[#]

- If there is no significant change, no action is required
- If there is a significant change, notify the AstraZeneca representative, who will inform the central Study Team, then follow the subsequent process described in Appendix B 5.
- A 'significant' change in the subject's condition refers to a clinically relevant change in any of the individual liver biochemistry parameters (ALT, AST or total bilirubin) in isolation or in combination, or a clinically relevant change in associated symptoms. The determination of whether there has been a significant change will be at the discretion of the Investigator, this may be in consultation with the Study Physician if there is any uncertainty.

E 7 Actions required for repeat episodes of potential Hy's Law

This section is applicable when a subject meets PHL criteria on study treatment, and has already met PHL criteria at a previous on study treatment visit.

The requirement to conduct follow-up, review, and assessment of a repeat occurrence(s) of PHL is based on the nature of the alternative cause identified for the previous occurrence.

The investigator should determine the cause for the previous occurrence of PHL criteria being met and answer the following question:

Was the alternative cause for the previous occurrence of PHL criteria being met found to be the disease under study (e.g., chronic or progressing malignant disease, severe infection or liver disease).

If No: Follow the process described in Appendix E 4.1.

If Yes: Determine if there has been a significant[#] change in the subject's condition compared with when PHL criteria were previously met.

If there is no significant change, no action is required.

If there is a significant change, follow the process described in Appendix E 4.

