A 'significant' change in the subject's condition refers to a clinically relevant change in any of the individual liver biochemistry parameters (ALT, AST or total bilirubin) in isolation or in combination, or a clinically relevant change in associated symptoms. The determination of whether there has been a significant change will be at the discretion of the Investigator; this may be in consultation with the Study Physician if there is any uncertainty.

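### Appendix E 6, and E 7 where the earlier episode was put down to the disease, can close a recurrence of potential Hy's Law after recovery as unchanged and so bypass the E 5 review

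*Protocol*

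**What the plan says.** Appendix E 2 defines PHL as AST or ALT at least 3 x ULN together with total bilirubin at least 2 x ULN, after study medication has started. E 4.2 sets the follow-up of a case: "Monitor the subject until liver biochemistry parameters and appropriate clinical symptoms and signs return to normal or baseline levels", or for as long as medically indicated. E 5 describes the joint review of cause and says that it applies to every case meeting the criteria. It is also where an SAE termed Hy's Law or Potential Hy's Law is raised.

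Two later sections deal with subjects who have met the criteria before.

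- **E 6** covers a subject who meets them on treatment "having previously met PHL criteria at a study visit prior to starting Study treatment". The investigator looks for a significant change "compared with the last visit where PHL criteria were met". The outcome is then: "If there is no significant change, no action is required".
- **E 7** covers a second on-treatment occurrence. It first asks whether the cause of the earlier one was "found to be the disease under study (e.g., chronic or progressing malignant disease, severe infection or liver disease"). If yes, the test is a significant "change in the subject's condition compared with when PHL criteria were previously met", again with no action if there is none. If no, the case is sent to E 4.1.

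For the liver tests, significance is defined as a "clinically relevant change in any of the individual liver biochemistry parameters (ALT, AST or total bilirubin) in isolation or in combination". Symptoms that go with them count in the same way. The investigator decides, and consulting the Study Physician is optional.

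**The concern.** Comparing one PHL occurrence with the previous one suits an elevation that has simply persisted. It does not suit a second rise after the first has settled, because the two peaks can look alike while the course between them does not. E 4.2 expects values to return to normal or baseline, so the protocol itself foresees that course.

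The information lost bears on causality. In both routes the earlier episode was not ascribed to olaparib: under E 6 it preceded treatment, and under this branch of E 7 it was put down to the disease. The recurrence may thus be the first occurrence in that subject for which the drug is a serious candidate. The disease category in E 7 includes severe infection, which can resolve and leave the old explanation out of date.

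AEs and SAEs are the primary endpoint of this trial (section 3), so a route by which a liver case can leave the reporting process matters even if it is seldom used.

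**Working it through.** The plan states no figure on this point, so the check is a trace of the decision rules for one pattern: PHL, recovery, PHL again at the same level.

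**Illustrative values (assumed, not from the protocol).** First episode: ALT 4 x ULN, bilirubin 2.5 x ULN. Recovery: both 1 x ULN. Second episode: ALT 4 x ULN, bilirubin 2.5 x ULN. Symptoms are unchanged. For the E 7 route, the first episode is assumed to have been attributed to the disease under study.

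| Comparator | ALT change (x ULN) | Bilirubin change (x ULN) |
|---|---|---|
| Earlier PHL occurrence (E 6, E 7) | 4 - 4 = 0 | 2.5 - 2.5 = 0 |
| Results in between | 4 - 1 = +3 | 2.5 - 1 = +1.5 |

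**Could the schedule show this pattern?** Table 1 has biochemistry on Days 29, 57, 85, 141 and 182. The gaps are 57 - 29 = 28, 85 - 57 = 28, 141 - 85 = 56 and 182 - 141 = 41 days. An episode, a recovery and a recurrence could fall on three consecutive scheduled visits.

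**Where the second episode goes:**

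1. E 6 (first episode before treatment): no biochemical change, so no action, unless symptoms differ or the investigator judges otherwise.
2. E 7, earlier cause the disease under study: the same result as 1.
3. E 7, any other earlier cause: the comparison is never made. The case goes to E 4.1, whose heading is for subjects who do not meet PHL criteria, although this subject does.
4. E 5 taken literally: the case is reviewed. This conflicts with 1 and 2, and nothing says which section prevails.

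**How often can E 6 apply?** The limits in section 5.1 are AST and ALT up to 2.5 x ULN (5 x ULN with liver metastases), and total bilirubin up to 1.5 x ULN unless direct bilirubin is within normal limits. Values of 3 x ULN and 2 x ULN at entry therefore need liver metastases together with raised total but normal direct bilirubin. E 2 also confines PHL to the time after study medication starts, which sits badly with a pre-treatment PHL visit.

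**What catches a closed case?** Section 8.4.1 requires every SAE to be reported. But section 8.3.7 makes deterioration in a mandated laboratory value an AE only if it meets a seriousness criterion or leads to discontinuation, and section 8.3.8 refers liver cases back to Appendix E. E 5 is where the medically important criterion and a related causality are assigned. For a laboratory finding without symptoms the fallback is weak.

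**The case against.** The strongest reply is that E 7 contains a deliberate exception. It opens by making review of repeat occurrences depend on the cause found for the earlier one. A subject reaches the comparison only after a cause has been identified, and E 5 brings the Study Physician and the sponsor's safety physician into that assessment. An earlier episode ascribed to olaparib, to another drug or to nothing certain never reaches the comparison. This stands, and it limits the point to the disease-attributed branch. It does not settle which of E 5 and E 7 governs, nor what happens when the earlier cause has resolved.

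A reader might infer that a closed case gets no sponsor attention and no SAE. The documents do not support that. E 3 has each new report meeting the thresholds notified to the sponsor's representative and entered in the CRF, a change in symptoms counts, the investigator has discretion, and section 8.4.1 still applies. What can be lost is the E 5 review and the SAE that it would raise.

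A reader might also see a contradiction with Appendix B 7, which asks "Did the AE reoccur if the suspected drug was reintroduced after having been stopped". B 7 guides a causality judgement and does not route cases. Its question concerns stopping and reintroducing the drug, which the pattern above does not require. It shows that the course between episodes is informative, and no more.

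**Conclusion.** The concern holds in a limited form. In E 6, and in E 7 when the earlier episode was attributed to the disease under study, the comparator ignores an intervening recovery. A recurrence at the same level can then end without the E 5 review and its SAE route, in conflict with the stated scope of E 5. This rests on a literal reading of E 6 and E 7, unchanged symptoms, and an investigator who does not use discretion the other way.

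Its size cannot be estimated, because the protocol gives no PHL rate. A reader might infer a known downward bias in the SAE proportion. One subject in about 200 is 1/200 = 0.5%, but that is the weight of a single postulated case and not a predicted frequency. The proportion would move only if the recurrence were not otherwise reported as serious, an E 5 review would have ended in an SAE, and the subject had no other SAE. None of these is shown. E 6 will rarely apply, so E 7 is the part that matters. This is a drafting gap worth closing, not a threat to the trial as a whole.

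**What to change.** Amend Appendix E so that E 4, E 5, E 6 and E 7 agree:

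- State that the judgement of significant change also takes account of results since the earlier occurrence, and that the no-action exit is for an elevation that has persisted, not for a recurrence after documented recovery. The sponsor should define recovery clinically, so that trivial fluctuation around a threshold does not trigger a new review.
- State whether E 5 or E 6/E 7 prevails for repeat occurrences.
- Reconcile the E 7 branch that sends a subject meeting PHL criteria to E 4.1. A change to the comparator alone would not touch this branch.
- Correct the E 6 reference to Appendix B 5, which concerns important medical events and contains no liver process.
- Reconcile the pre-treatment PHL of E 6 with the E 2 definition.

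The change concerns case assessment and reporting only and uses results already collected. The cost is the amendment text and a few extra case reviews.

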Appendix F Abbreviations

Abbreviation or special term	Explanation
AE	Adverse event
ALT	Alanine Aminotransferase
AML	Acute Myeloid Leukemia
APTT	Activated Partial Thromboplastin Time
AST	Aspartate Aminotransferase
BD	Twice daily
BP	Blood pressure
BRCA	Breast cancer susceptibility gene
BUN	Blood Urea Nitrogen
CI	Confidence Interval
CR	Complete response
CrCl	Creatinine clearance
eCRF	Electronic case report form
CSA	clinical study agreement
CSR	clinical study report
CTCAE	Common Terminology Criteria for Adverse Event
DAE	discontinuation of study drug due to adverse event
DNA	deoxyribonucleic acid
DOT	Duration of response
DSB	Double stranded breaks
EC	Ethics committee, synonymous to institutional review board (IRB) and independent ethics committee (IEC)
ECOG	Eastern Cooperative Oncology Group
EU	European Union
FAS	Full analysis set
FSI	First subject in
gBRCAm	Germline BRCA mutation
GCP	Good Clinical Practice
G-CSF	Granulocyte Colony Stimulating Factor
Hb	Haemoglobin

Abbreviation or special term	Explanation
HR	Hazard ratio
ICH	International Conference on Harmonisation
INR	International Normalized Ratio
HRR	Homologous Recombination Repair
MCV	Mean Cell Volume
MDS	Myelodysplastic syndrome
MBC	Metastatic Breast Cancer
NHEJ	Non – homologous end junction
OAE	Other significant adverse event
OC	Ovarian Cancer
PARP	Poly-adenosine 5'diphosphoribose (ADP) Polymerase
PD	Progression of disease
PFS	Progression free survival
PI	Principal investigator
p.o.	Administration by mouth
PR	Partial response
PSR	Platinum Sensitive Relapsed
QoL	Quality of Life
RECIST	Response Evaluation Criteria in Solid tumours version 1.1.
SAE	serious adverse event
SAP	statistical analysis plan
SD	Stable disease
ULN	Upper limit of normal
US	United States of America
WBDC	Web based data capture

ASTRAZENECA SIGNATURE(S)

A prospective, multicentre, Phase-IV clinical trial of Olaparib in Indian patients with platinum sensitive relapsed ovarian cancer who are in complete or partial response following platinum based chemotherapy and metastatic breast cancer with germline BRCA1/2 mutation (SOLI study)

This Clinical Study Protocol has been subjected to an internal AstraZeneca review

I agree to the terms of this Study protocol.

AstraZeneca representative

PPD

